### 3.4 Removal of patients from study

A patient who withdraws is one who discontinues participation in a clinical study for any reason.

Patients may be withdrawn from the trial for the following reasons:

- At their own request or at the request of their legally acceptable representative
- If, in the investigator's opinion, continuation in the study would be detrimental to the patient's well-being
- At the specific request of the sponsor

Patients must be withdrawn also for the following reasons:

- In case of unacceptable toxicity or progressive disease
- In case of substantial non-compliance with the requirements of the study
- Positive beta-HCG test consistent with pregnancy. Pregnancy will be reported along the same time lines as a serious adverse event

- Use of illicit drugs or other substances that may, in the opinion of the investigator, have a reasonable chance of contributing to toxicity or otherwise skewing results
- Development of an intercurrent illness or situation which would, in the judgment of the investigator, affect assessments of clinical status and study endpoints to a significant degree
- Development of a second cancer that requires treatment
- Patient is lost to follow-up
- Interruption in study drug administration for a period longer than 28 consecutive days
- Patient death

Relevant visit data will be entered into the CRF, and any unused study medication will be accounted for and returned for all subjects entered into the trial even if for a brief period of time. Subjects who discontinue study treatment will have relevant information completed and recorded in the CRF and medical record. All subjects who discontinue because of adverse events or clinical laboratory abnormalities should be followed up until they recover or stabilize and the subsequent outcome recorded.

In case of premature withdrawal of any cause, all data documented up to the date of withdrawal will be entered into the study analysis.

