##### 4.1.5.1 Dose modification for hematological toxicity

Hematological toxicities will be considered not relevant for dose modification during the period of chemotherapy and the expected subsequent myelosuppression. However, these criteria will apply after hematopoietic recovery from the last chemotherapy course during the subsequent maintenance therapy.

Toxicity	Grade 1	Grade 2	Grade 3*	Grade 4*
Hematologic	Continue at the same dose level.	Continue at the same dose level.	Withhold dose until toxicity is grade <2, then resume treatment at the same dose level. If patient experiences a second grade 3 toxicity, withhold dose until toxicity is grade <2, then reduce dose to 400 mg p.o. QD and resume treatment.	Withhold dose until toxicity is grade <2, then reduce dose to 400 mg p.o. QD and resume treatment, or discontinue at the discretion of the principal investigator after discussion with study sponsor (safety desk at SAL).

\*Patients who develop grade 3 leukopenia, or grade 3/ grade 4 lymphopenia may continue Sorafenib/ Placebo treatment without interruption at the discretion of the investigator.

Table 3: Dose modifications and delays for hematologic toxicities of Sorafenib/ Placebo

Table 4 summarizes the recommendations for dose delays and modifications for all non-hematologic adverse events, except for skin toxicities and hypertension, which will be detailed separately (Table 5, Table 6, Table 7). These recommendations pertain, if the adverse event is considered to be related to Sorafenib/ Placebo, but not to the chemotherapy.

Toxicity	Grade 1	Grade 2	Grade 3*	Grade 4*
Non-hematologic	Continue at the same dose level.	Continue at the same dose level.	Withhold dose until toxicity is grade <1, then resume treatment at the same dose level. If patient experiences a second grade 3 toxicity, withhold dose until toxicity is grade <1, then reduce dose to 400 mg p.o. QD and resume treatment.	Withhold dose until toxicity is grade <1, then reduce dose to 400 mg p.o. QD. and resume treatment, or discontinue at the discretion of the principal investigator after discussion with study sponsor.

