*Patients who develop grade 3 fever/ chills, grade 3 elevation of hepatic transaminases with ALT and AST <10x ULN, grade 3 hyperlipasemia or hyperamylasemia without clinical or other evidence of pancreatitis may continue Sorafenib/ Placebo treatment without interruption at the discretion of the investigator. Also excludes nausea/ vomiting that has not been premedicated, and diarrhea. If no recovery after 30 day delay, treatment will be discontinued unless patient is deriving clinical benefit. If more than 2 dose reductions are required, treatment will be discontinued.				

*Table 4: Dose modifications for Sorafenib-associated non hematological toxicity except hand-foot skin reactions and hypertension*

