#### 4.1.5.3 Dose modifications for hypertension

An increased incidence of hypertension was observed in Sorafenib-treated patients. Hypertension was usually mild to moderate, occurred early in the course of treatment, and was amenable to management with standard antihypertensive therapy. Blood pressure should be monitored regularly and treated, if required, in accordance with standard medical practice. In cases of severe or persistent hypertension, or hypertensive crisis despite adequate antihypertensive therapy, permanent discontinuation of Sorafenib/ Placebo should be considered. In general, hypertension should be treated according to Table 7.

Management of treatment-emergent hypertension	
Grade of Event (CTCAE v3)	Management / next dose
Grade 1: asymptomatic and transient	Consider increased BP monitoring
Grade 2: asymptomatic and diastolic BP < 110 mmHg	Begin anti-hypertensive therapy and continue Sorafenib/ Placebo
Grade 2: symptomatic / persistent OR Diastolic BP ≥ 110 mmHg OR Grade 3	Sorafenib/ Placebo should be stopped* until symptoms resolve and diastolic BP returns to ≤ 100 mmHg. Treat subject with anti-hypertensives. When Sorafenib/ Placebo is re-started, reduce to 400 mg p.o. QD and possibly re-escalate dose later at the discretion of treating physician. If diastolic BP is not controlled to ≤ 100 mmHg on therapy, reduce Sorafenib/ Placebo to 400 mg p.o. every other day (QOD) and monitor BP closely If BP is not controlled on Sorafenib/ Placebo 400 mg p.o. QOD, study treatment should be discontinued
Grade 4: life-threatening	Discontinue Sorafenib/ Placebo permanently (end of study)
Please note the distinction between asymptomatic and symptomatic grade 2 hypertension. * Subjects requiring a delay of > 28 days should go off protocol therapy (end of study).	

*Table 7: Suggested dose modifications for Sorafenib/ Placebo-associated hypertension*

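### Section 3.4, Table 7 and 4.3.3.1 tie a study-drug tolerance limit to leaving the study, other sections end treatment only, and EFS follow-up after such a stop is not ordered.

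*Protocol*

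**What the plan says.** Section 3.4 lists reasons for which a patient must be withdrawn. One of them is "Interruption in study drug administration for a period longer than 28 consecutive days". The section opens by defining the term: "A patient who withdraws is one who discontinues participation in a clinical study for any reason". After premature withdrawal, "all data documented up to the date of withdrawal will be entered into the study analysis". Patients who discontinue because of adverse events or laboratory abnormalities "should be followed up until they recover or stabilize and the subsequent outcome recorded". No other clinical follow-up after withdrawal is ordered there.

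The Table 7 footnote on hypertension says: "Subjects requiring a delay of > 28 days should go off protocol therapy (end of study". Its grade 4 row also equates permanent discontinuation of the drug with end of study. Section 4.3.3.1, under Arm V, excludes a patient from the study if more than two levels of dose reduction are needed.

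Other places are milder. Section 4.1.5 discontinues study treatment when a dose below 400 mg every other day would be required. The Table 4 footnote says "If more than 2 dose reductions are required, treatment will be discontinued" and, on delays, "If no recovery after 30 day delay, treatment will be discontinued unless patient is deriving clinical benefit". Its introduction reads "Table 4 summarizes the recommendations for dose delays and modifications for all non-hematologic adverse events", with skin toxicity and hypertension handled separately.

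Section 7.2 promises an ITT analysis of every randomized patient, whether or not study medication was received. Section 7.2.1 censors EFS at the last follow-up examination for a patient without an event. Table 15 counts the follow-up visits from the end of maintenance, and 4.3.4 gives maintenance only after three consolidation courses.

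**The concern.** EFS under ITT needs relapse and death to be observed whether or not the patient still takes the tablets. If a toxicity stop is treated as leaving the study, visits end, and 7.2.1 then censors an event-free patient at the last examination. The reason for that censoring is drug toxicity, which may depend on both arm and prognosis, so it need not be independent of the later event. The log-rank comparison assumes that it is.

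The different time limits add a second source of variation. A patient on day 29 of a hold for drug-related liver toxicity must leave under 3.4 but may remain on treatment under Table 4. Section 3.4 is mandatory and Table 4 is phrased as recommendations, but no order of precedence is given. At stake are the completeness of the confirmatory endpoint and consistent handling across sites.

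**Working it through.** **1. The rules side by side**

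| Place | Trigger | What ends |
|---|---|---|
| 3.4 | more than 28 consecutive days off drug | study participation (mandatory) |
| Table 7 footnote | delay over 28 days | protocol therapy, glossed as end of study |
| Table 7, grade 4 | life-threatening hypertension | drug, glossed as end of study |
| 4.3.3.1 | more than 2 levels of dose reduction | patient leaves the study |
| 4.1.5 | dose below 400 mg every other day needed | study treatment |
| Table 4 footnote | more than 2 dose reductions | treatment |
| Table 4 footnote | no recovery after 30 days, unless benefit | treatment |

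Table 2 has three dose levels, so more than two reductions means going below 400 mg every other day. Sections 4.1.5, Table 4 and 4.3.3.1 therefore describe the same dose limit with two different consequences. The time limits differ on days 29 and 30 of a hold covered by Table 4, and after day 30 only for a patient deriving clinical benefit.

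**2. The plan's own figures**

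Inputs from 7.1: medians of 9 and 13.5 months, two-sided alpha 0.05, power 80%, accrual 24 months, follow-up 18 months, loss hazard 0.0074 (read as per month).

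- Events: 4 × (1.960 + 0.842)² / (ln(9/13.5))² = 4 × 7.849 / 0.1644 = 191, as stated.
- Event probability with exponential EFS and uniform accrual: 0.827 control, 0.711 Sorafenib, mean 0.769. Then 191 / 0.769 = 248, against the stated 250.

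The planned size reproduces, so the same model is used below.

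**3. Events that would go unseen**

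For a patient withdrawn event-free at month t, the probability of an event by month 18 is 1 − exp(−(ln 2 / m) × (18 − t)). Here t = 4 is an assumption (range 2 to 6), and the arm's own median m is kept after withdrawal.

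- Control, m = 9: 0.660, or 6.6 per 10 patients (7.1 to 6.0).
- Sorafenib, m = 13.5: 0.513, or 5.1 per 10 patients (5.6 to 4.6).

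**4. Illustration of bias**

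Simulation with 1,500,000 patients per arm: exponential EFS, administrative censoring uniform between 18 and 42 months, loss hazard 0.0074, Cox hazard ratio. A share q of patients event-free at month 4 is withdrawn and afterwards has k times the control hazard. Both q and k are assumptions. Unlike step 3, this removes the Sorafenib benefit after withdrawal.

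| Withdrawn at month 4 | k | HR, follow-up continued | HR, censored at withdrawal |
|---|---|---|---|
| 5% Sorafenib only | 1 / 2 | 0.676 / 0.690 | 0.666 |
| 10% Sorafenib only | 1 / 2 | 0.686 / 0.715 | 0.666 |
| 20% Sorafenib only | 1 / 2 | 0.706 / 0.767 | 0.667 |
| 10% Sorafenib, 5% control | 2 | 0.701 | 0.667 |
| 10% both arms | 1 / 2 | 0.687 / 0.687 | 0.667 |

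Moving the 10% Sorafenib-only withdrawal to month 2 or month 6 gives 0.689 or 0.683 for k = 1, and 0.723 or 0.708 for k = 2.

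**5. Scale**

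The standard error of the log hazard ratio at 191 events is 2 / √191 = 0.145. For 10% in the Sorafenib arm only, the shift is ln(0.686 / 0.666) = 0.030, or 0.2 standard errors, for k = 1. For k = 2 it is ln(0.715 / 0.666) = 0.071, or 0.5 standard errors.

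**The case against.** The strongest reply is that 3.4 is an off-treatment list in loose wording. It also contains progressive disease, loss to follow-up and death. If withdrawal ended all observation, OS could not be observed after progression, yet OS is a secondary objective and 7.2.1 censors it only when the patient was last known alive. The sentence on data up to withdrawal says what is entered; it does not say that later data are excluded. This stands: the documents do not support the stronger inference that the plan orders censoring at a drug stop and gives up ITT. What remains is that the definition in 3.4, Table 7 and 4.3.3.1 point the other way, and nothing in 7.2 or 7.2.1 orders collection after a stop. An analysis plan cannot recover relapses that were never recorded.

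A reader might also infer that patients stopped early have no visits at all. That goes too far. The Table 14 assessments are tied to chemotherapy courses, so a patient who stops only the tablets but continues high-dose cytarabine is still examined. Section 5.1.3 lists blood count and performance status every 3 months without naming a population. The real gap is the missing starting point for long-term visits in patients who never reach maintenance.

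On size, withdrawal in one arm only is an assumption that favours finding bias. The protocol's one comparative discontinuation figure, from the renal cell cancer trial, is nearly equal between arms (10% and 8%). Nothing in the document supports a doubled hazard after withdrawal. The hazard ratio of 0.77 needs 20% withdrawal, in one arm, with that doubled hazard.

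**Conclusion.** The inconsistency is in the text and touches the confirmatory endpoint, so it should be fixed. Its effect is probably modest. With 10% of patients event-free at month 4 withdrawn, censoring gives a hazard ratio of about 0.67. Continued follow-up gives about 0.69 to 0.72 if only the Sorafenib arm is affected and about 0.69 if both arms are affected equally. In these scenarios censoring flatters Sorafenib. The figures rest on assumed withdrawal shares, timing and later hazards, because the protocol gives no rate of such stops for this population.

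A reader might infer a loss of power. The documents do not show one: the planned size reproduces, and the 0.0074 hazard and the allowance for up to 25 patients cover some lost numbers. They do not address bias. The 28-day against 30-day mismatch is by itself a small matter of harmonization; the benefit exception is its sharper part.

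**What to change.** - State in 3.4, Table 7 and 4.3.3.1 that reaching an interruption or dose-reduction limit ends study drug only, and that EFS and OS follow-up continues and enters the ITT analysis. Keep withdrawal from the study for patients who refuse further follow-up.
- Give patients who never reach maintenance a follow-up anchor once their Table 14 chemotherapy visits end, for example the 5.1.3 blood count and performance status every 3 months.
- Use one time limit and one benefit exception in 3.4, Table 4 and Table 7. The clinical team should set the limit.

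The cost is amendment wording and a few routine follow-up visits for early stoppers. No additional patients are needed.

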## 5.2 Schedule of evaluations

	Within 10 days prior to the first course of induction therapy	Between day 1 and day 22 of first course of induction chemotherapy	Early response evaluation (d 16)	Before the second course of induction therapy	From day 1 of second course of induction chemotherapy until start of consolidation therapy	Remission control – latest 35 days after the beginning of second induction	Before each course of consolidation therapy	From the beginning of first course of consolidation until the end of third course of consolidation = beginning of maintenance therapy	Postremission control latest day 35 after begin of each course of consolidation therapy
Informed consent	X								
Medical history	X								
Performance status and physical examination	X			X			X		
Vital Signs (blood pressure and pulse) a	X	Daily measurement of blood pressure		X	weekly		X	weekly	
Body weight and height	X			X			X		
CBC (with differential and platelets) a	X	3 times / week		X	weekly	X	X	weekly	X
Chemistry and coagulation a	X	3 times / week		X	weekly		X	weekly	

	Within 10 days prior to the first course of induction therapy	Between day 1 and day 22 of first course of induction chemotherapy	Early response evaluation (d 16)	Before the second course of induction therapy	From day 1 of second course of induction chemotherapy until start of consolidation therapy	Remission control – latest 35 days after the beginning of second induction	Before each course of consolidation therapy	From the beginning of first course of consolidation until the end of third course of consolidation = beginning of maintenance therapy	Postremission control latest day 35 after begin of each course of consolidation therapy
ECG and echocardiography a	X			X			X		
Pregnancy test e	X								
Bone marrow aspirate	X		X			X			X b
Bone marrow biopsy	X								
Bone marrow and blood samples for exploratory research	X		X			X			X b

Table 14: Schedule of evaluation I (prior to and during induction/ consolidation therapy)

	Start of maintenance therapy	During maintenance therapy	End of maintenance therapy	Follow-up 3, 6, 9, 12, 15 and 18 months after end of maintenance therapy	Relapse (during study treatment or follow-up)
Performance status and physical examination	X	monthly	X	X	
Vital Signs (blood pressure and pulse) a	X	monthly	X		

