## **7.2 Statistical Analysis Plan**

We assume an accrual time of 24 months and a follow-up time of 18 months.

The statistical analysis will be performed according to the intention to treat principle (ITT analysis). This means that every patient included into the study and randomized to one treatment arm will be evaluated in that arm, even if he does not receive study-medication, or if any other violations of the study protocol occur.

- The primary endpoint (median EFS) will be compared between both treatment arms using two-sided stratified log-rank test as described in detail. This part of the analysis is considered as confirmatory.
- Analyses of secondary endpoints will include morphologic CR-rate, overall survival, leukemia free interval and leukemia free survival.
- In an exploratory approach EFS and OS will be analyzed using stratified Cox-regression. Treatment arm and cytogenetic findings will be included as independent variables. The results of these analyses will be considered as exploratory. No  $\alpha$ -adjustment will be performed.
- In addition to the ITT-analysis a per protocol analysis (PP-analysis) will be performed. This analysis will include only those patients who could be treated with full adherence to the protocol. Besides this, the PP-analysis will parallel the ITT-analysis.

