***Treatment failure:***

Partial Remission (PR):

- Platelet count >100.000/μl
- Granulocyte count of >1.000/μl
- Bone marrow (aspirate with marrow spicules): Decrease of at least 50% in the percentage of blasts to 5% - 25%

Resistant disease:

- Patient survives ≥ 7 days post Chemotherapy (CT); persistent AML in blood or bone marrow

Death in Aplasia:

- Patient survives ≥ 7 days post Chemotherapy (CT); death while cytopenic, with aplastic bone marrow

Indeterminate cause:

- Patients who die < 7 days post CT; Patients who die > 7 days post CT with no PB blasts, but no bone marrow examination; Patients who do not complete the first course of therapy

Morphologic relapse:

- Reappearance of blasts post CT in PB or bone marrow

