***Definition of Study Endpoints***

Complete remission rate (CR rate):

Proportion of patients in complete remission (CR, as defined above) after induction chemotherapy.

Event free survival (EFS):

Time interval from day 1 of study treatment until

- treatment failure (no CR/ CRi 5 weeks after the beginning of the second induction therapy course),
- relapse from CR
- relapse from morphologic leukemia-free state (CRi)
- death from any cause

whichever occurs first. The time point at which the patient is resistant to therapy or survives induction without a CR or Morphologic leukemia-free state will be noted. For a patient with none of these events before the end of study follow-up, observation of EFS will be censored at the date of his or her last follow-up examination.

Overall survival (OS):

Time interval from day 1 of study treatment to the day of death. For a patient who is not known to have died by the end of follow-up, observation of OS will be censored on the date the patient was last known to be alive.

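### Section 3.4 treats stopping study drug as leaving the study and schedules no relapse or survival follow-up for early stoppers, in conflict with the ITT principle and the endpoint rules

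*Protocol*

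**What the plan says.** Protocol 3.4 defines withdrawal as leaving the study: "A patient who withdraws is one who discontinues participation in a clinical study for any reason". Its list of mandatory withdrawals includes "In case of unacceptable toxicity or progressive disease", "In case of substantial non-compliance with the requirements of the study" and a study-drug interruption of more than 28 consecutive days. The section closes with "In case of premature withdrawal of any cause, all data documented up to the date of withdrawal will be entered into the study analysis". The only later follow-up it names concerns patients who discontinue for adverse events or laboratory abnormalities, until these recover or stabilise.

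Two other places merge the drug with the study. The note to Table 7 (4.1.5.3) equates a delay of more than 28 days with the end of the study. The text under Table 13 (4.3.3.1) excludes from the study a patient who needs more than two levels of dose reduction.

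Table 15 (5.2) heads its follow-up column "Follow-up 3, 6, 9, 12, 15 and 18 months after end of maintenance therapy". Under 4.3.4, maintenance is given only to patients who received three consolidation courses.

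Section 7.2 promises that every randomised patient is evaluated in the assigned arm, "even if he does not receive study-medication, or if any other violations of the study protocol occur". In 7.2.1, EFS is censored at the last follow-up examination and OS when the patient was last known to be alive. Withdrawal is not named as a censoring event. The EFS failure event is "no CR/ CRi 5 weeks after the beginning of the second induction therapy course", whereas the treatment-failure list in the same section includes "Patients who do not complete the first course of therapy".

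**The concern.** An intention-to-treat analysis of EFS and OS needs relapse and death dates for all randomised patients, whether or not they still take study drug. A site that follows 3.4 and Table 15 would end participation when drug stops for toxicity, non-compliance or a long interruption, and would have no visit at which to record later relapse or death. An analysis plan written afterwards cannot recover data that sites were never asked to collect.

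The listed reasons for withdrawal may be related both to treatment arm and to prognosis. If they are, ending observation at withdrawal is informative censoring, and the comparison drifts towards the effect in patients who tolerate the drug. Overall survival, a secondary objective in 2.3.2, is the more exposed endpoint: withdrawal at progression would end observation before many leukaemia deaths. The confirmatory endpoint, EFS, is exposed through withdrawals that come before an event.

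**Working it through.** **1. The passages side by side**

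| Question | 3.4, Table 7 note, text under Table 13, Table 15 | 7.2 and 7.2.1 |
|---|---|---|
| Does stopping drug end participation? | Yes, for the mandatory reasons | No: evaluated in the assigned arm regardless |
| Which data enter the analysis? | Those documented by the withdrawal date | Up to the last examination (EFS) or date last known alive (OS) |
| Scheduled follow-up if drug stops before maintenance? | None that can be dated; only recovery from adverse events or laboratory changes | Needed for both endpoints |
| Alive, leaves induction without CR/CRi, no second course? | Withdrawn | In the treatment-failure list if the first course was not completed, but the EFS failure rule is never reached |

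**2. Which endpoint each reason touches**

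- Relapse, and failure five weeks after the start of the second induction, are EFS events. A patient withdrawn at relapse already has the EFS event, so this costs OS only.
- Progressive disease is not defined in 7.2.1. It can cut EFS only if it leads to withdrawal in induction before the failure time point.
- Toxicity, non-compliance and the 28-day rule can cut both EFS and OS.

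**3. The plan's own figures reproduce**

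Inputs from 7.1: medians 9 and 13.5 months, two-sided alpha 0.05, power 80%, 1:1 allocation, accrual 24 months, follow-up 18 months, loss hazard 0.0074 (taken as per month).

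- Hazard ratio under exponential EFS: 9/13.5 = 0.667.
- Events (Schoenfeld): 4 × (1.960 + 0.842)² / (ln 0.667)² = 191, as stated.
- Mean event probability with the loss hazard: 0.769. N = 191/0.769 = 248, against the stated 250.
- With 276 patients: 276 × 0.769 = 212 events. Power = Φ(√212 / 2 × 0.405 − 1.96) = 84.0%.

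The point does not rest on an arithmetic error.

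**4. Loss of events if observation stops at withdrawal**

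The protocol gives no withdrawal rate. The shares below are assumptions, applied equally in both arms on top of the 0.0074 hazard, with 276 patients.

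| Withdrawn by 12 months | EFS events | Power |
|---|---|---|
| 5% | 204 | 82.4% |
| 10% | 195 | 80.8% |
| 15% | 187 | 79.1% |
| 20% | 179 | 77.3% |
| 30% | 162 | 73.3% |

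**5. Bias if withdrawal carries prognostic information**

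Simulation with event hazard ln 2/9 per month in both arms while on study (no drug effect), withdrawal uniform over months 1-9, the hazard multiplied by k after withdrawal, and administrative censoring at 18-42 months. The Cox hazard ratio (Sorafenib/placebo) with everyone followed is compared with the one obtained when data are cut at withdrawal.

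| Sorafenib vs placebo withdrawn | k | HR, all followed | HR, cut | Events lost |
|---|---|---|---|---|
| 15% vs 10% | 1.5 | 1.01 | 1.00 | 9% |
| 15% vs 10% | 3 | 1.03 | 1.00 | 10% |
| 15% vs 5% | 1.5 | 1.02 | 1.00 | 7% |
| 15% vs 5% | 3 | 1.05 | 1.00 | 8% |
| 25% vs 10% | 1.5 | 1.04 | 1.00 | 12% |
| 25% vs 10% | 3 | 1.09 | 1.00 | 13% |
| 25% vs 5% | 1.5 | 1.05 | 1.00 | 11% |
| 25% vs 5% | 3 | 1.11 | 1.00 | 11% |
| 10% vs 8% | 1.5 to 3 | 1.00 to 1.01 | 1.00 | 6 to 7% |

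With k = 1 the two hazard ratios agree at 1.00 in every row, so only events are lost.

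With an on-study hazard ratio of 0.667 and heavier assumptions (20-30% against 10% withdrawn by 12 months, k from 1.5 to 3), the followed hazard ratio is 0.69-0.80 and the cut one 0.66-0.67.

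**The case against.** The strongest reply is that the closing sentence of 3.4 is a retention rule: it stops sites from discarding withdrawn patients. It does not say that only these data count, and 7.2.1 does not censor at withdrawal. A reader might infer that later relapses and deaths are dropped by rule. The text does not go that far. What stands is that the passages conflict and that nothing schedules the collection of those data.

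The wording is also uneven. Section 3.4 has a separate sentence on patients who discontinue study treatment, and 4.1.5 and 4.3.3.1 in places speak of ending treatment, not the study. Section 5.1.3 lists three-monthly blood counts and performance status without tying them to maintenance. Table 15 does tie them, so these passages add to the ambiguity and do not settle it.

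A reader might also infer that the rule is shown to favour Sorafenib. It is not. The only comparative figure in the protocol, from the renal-cell trial in 6.3.1.5, is permanent discontinuation for adverse events of 10% on Sorafenib and 8% on placebo. That is a different disease without chemotherapy, so it is not decisive, but at those rates the shift is about 0.01. At 191 events the standard error of the log hazard ratio is about 2/√191 = 0.145, larger than every null-case shift in the table in step 5.

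Nor do the documents support the inference that OS cannot be answered. Section 6.1 requires deaths, including those from progression, to be reported during protocol treatment and for 30 days after it. Deaths beyond that window are the gap.

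Finally, 7.1 budgets a loss hazard and up to 25 losses, counting protocol violation among them. This answers part of the lost power but none of the bias. Censoring at transplantation is a separate design choice and is not counted here.

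**Conclusion.** The point holds as a contradiction between 3.4 (with the Table 7 note, the text under Table 13 and Table 15) and 7.2 with 7.2.1, together with missing relapse and survival follow-up for patients who stop before maintenance. OS is affected by every withdrawal reason, progression above all. EFS is affected mainly by toxicity, non-compliance or interruption before an event, and by patients who leave induction without CR/CRi before a second course. It would be wrong to read withdrawal at progression as a general truncation of EFS, because relapse and second-induction failure are already events.

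The size rests on assumed rates and prognosis. Under 15-25% against 5-10% withdrawn and a 1.5-3 times higher later hazard, 7-13% of EFS events are lost and a followed hazard ratio of 1.01-1.11 reads as about 1.00. Under 10% against 8% the bias is about 0.01, and under uninformative withdrawal it is nil. Direction and size are therefore plausible, not shown. The contradiction and the missing follow-up do not depend on these assumptions.

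**What to change.** - In 3.4, separate discontinuation of study drug from withdrawal of consent. State that all randomised patients are followed for relapse and survival to the common cut-off unless consent is withdrawn, and that these data enter the intention-to-treat analysis. Replace the closing sentence on withdrawal data accordingly.
- In Table 15, anchor the three-monthly follow-up to the end of study treatment for every patient, and bring 5.1.3 into line.
- Align the note to Table 7 and the text under Table 13, so that they refer to study treatment and not to the study.
- In 7.2.1, reconcile the treatment-failure list with the EFS definition, so that leaving induction without CR/CRi is an EFS event whether or not a second course started.

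The cost is protocol wording plus some added follow-up contacts and data entry. The planned 191 events, 250 evaluable patients and accrual of 276 stay as they are. No change to when treatment is stopped is proposed.
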